5.0 Study Outcomes and Study Measures

5.1 Primary Outcome

5.1.1 The primary outcome of this study is the mean visual analog scores (scale of 0-10) within the first 48 hours postoperatively. This will be measured every 12 hours for the first 48 hours and will be assessed by the level of breast pain associated with arm movements while eating.

5.1.1.1 Visual analog scores in mastectomy patients with oral and IV narcotics are approximately 5.0 at 24 hours and 4.8 at 48 hours¹⁷

5.1.1.2 For patients with local infiltration of Liposomal bupivacaine after implant based reconstruction, visual analog scores at 24hrs were 3.8 on average¹⁸

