6.1 Study-Related Activities

Patient involvement in the study will be initiated in the plastic surgery clinic. Eligible subjects will be identified prior to surgery. Potential subjects will be contacted either by phone or during their clinic visit, informed consent will be obtained and a 30-minute preoperative assessment will be performed. Patients will be informed that if they are expected to undergo an axillary lymph node dissection at the time of surgery then they will be excluded from the study. Patients who are undergoing sentinel lymph node biopsies will be included in the study, but if their nodes are positive and there is an intraoperative decision to pursue axillary lymph node dissection they will subsequently be excluded from the study. Also, we will record demographic and history information, including existing pain elsewhere, and administer questionnaire-based measures of psychological state, physical function, and baseline pain (Table 1, Appendix F). Questionnaire responses will be entered via the cancer center REDCap data entry form. From these questionnaires, we will place each participant on a dimensional continuum that describes their general cognitive style. We will use multidimensional scaling (MDS) to force catastrophizing and optimism as 2 ends of this continuum.

Table 1. Preoperative Questionnaires

Life Orientation Test-Revised (LOT-R)

PROMIS- Depression

PROMIS- Anxiety

Pain Catastrophizing Scale (PCS)

**THE USE OF LIPOSOMAL BUPIVACAINE FOR PAIN CONTROL FOLLOWING
MASTECTOMY AND IMMEDIATE IMPLANT BASED BREAST RECONSTRUCTION**

Wake Forest Baptist Comprehensive Cancer Center
CCCWU # 99517

[figure not shown]
These two constructs describe cognitive styles that are strongly inversely associated with each other; MDS will provide the optimal weights to best order individuals on this latent scale. Studies have examined the interplay of these constructs with other psychological concepts such as acceptance, pain-related disability and psychosocial adjustment and have found that both are reliably associated with the positive and negative aspects of the adjustment to pain.

The research coordinator will then assign the patients a study number. On the day of surgery, each patient will be randomized to be in one of the following two groups for perioperative local anesthetic infiltration:

1. Local infiltration of bupivacaine
2. Local infiltration of liposomal bupivacaine

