10.0 Statistical Considerations

10.1 Analysis of Primary Objective

10.1.1 The study will allow for an attrition rate of 10%. Assuming a similar standard deviation in pain score at 48 hours for the local infiltration of liposomal bupivacaine and bupivacaine arms, with a 2-sided alpha of 0.05 and power of 80%, the study would have the ability to detect an effect size (absolute value of difference in sample means divided by the standard deviation) of 0.6 between the 2 groups with 25 subjects per arm. We will recruit 25 subjects per arm; if there is no attrition, with the same alpha and power as above, the study would have the ability to detect an effect size of 0.57. The primary outcome will be the pain score observed at 48 hours. To test for differences in these scores between the 2 arms, an independent t-test will be used; if the observed p-value is <0.05, statistical significance will be assumed. Two-sided ANOVA will be performed for statistical analysis once data collection is complete.

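### The primary test is valid but unadjusted; pre-specifying the preoperative Pain Catastrophizing Scale as a covariate could narrow the interval at almost no cost

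*Combined protocol and SAP*

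**What the plan says.** Section 10.1.1 gives the primary analysis in two sentences. The first reads "To test for differences in these scores between the 2 arms, an independent t-test will be used", with significance declared at p below 0.05. The second reads "Two-sided ANOVA will be performed for statistical analysis once data collection is complete". Neither names a covariate, and no adjusted primary analysis appears elsewhere.

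The PCS is scheduled for the preoperative visit (calendar in 6.0), listed in Table 1 of 6.1, stored in REDCap (9.0) and printed in Appendix F. Allocation comes later: "On the day of surgery, each patient will be randomized". On optimism and catastrophizing, 6.1 says that "both are reliably associated with the positive and negative aspects of the adjustment to pain". The only planned analytic use is in 5.2.6.3 and 10.2.6.2, where an optimism-catastrophizing continuum is explored as a predictor of the pain trajectory.

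The primary endpoint has two definitions. Section 10.1.1 says "The primary outcome will be the pain score observed at 48 hours", while 5.1.1 says "The primary outcome of this study is the mean visual analog scores (scale of 0-10) within the first 48 hours postoperatively".

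**The concern.** With two arms, an ANOVA without covariates is the same comparison as the t-test, so both sentences in 10.1.1 describe one unadjusted analysis. The trial already collects, before randomisation, a score that the protocol treats as a candidate predictor of pain, and the primary analysis leaves it out.

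What is at stake is efficiency, not bias. With 25 per arm the 95% interval for the difference is wide, at plus or minus 0.57 SD. A baseline score related to early pain would remove some residual variance. Naming it in advance would also prevent a later choice among the several preoperative questionnaires.

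**Working it through.** **Inputs from the plan (10.1.1, 10.3).** 25 per arm, two-sided alpha 0.05, target effect 0.6 SD and 10% attrition. No raw SD is given, so the SD is set to 1. Attrition leaves 25 × 0.9 = 22.5, taken as 22 per arm.

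**Assumed input.** r, the within-arm correlation of the PCS total with the primary pain outcome. The documents do not give it; the range used is 0 to 0.5.

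**The plan's own figure.** 10.1.1 claims 80% power for 0.6 SD with 25 per arm. This does not reproduce. The exact t calculation gives 54.7% power, and the effect detectable with 80% power is 0.81 SD. An effect of 0.6 needs 45 per arm and 0.57 needs 50; 45/0.9 = 50. The stated effect sizes fit 45 completers out of 50 recruited per arm. That needs its own correction; here 54.7% is the baseline.

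**Unadjusted.** df = 2n − 2 = 48 and t = 2.0106. Half-width = 2.0106 × √(2/25) = 0.569 SD. Noncentrality = 0.6 × √(25/2) = 2.121, giving power 54.7%.

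**Adjusted for one covariate.** df = 2n − 3 = 47 and t = 2.0117. The variance of the difference is multiplied by (1 − r²)(1 + 1/(2n − 4)); the last factor, 1 + 1/46, allows for chance imbalance in the PCS. So half-width = 2.0117 × √[(2/25)(1 − r²)(1 + 1/46)]. At r = 0.3 this is 0.549, and 0.549/0.569 gives the 3.5% reduction.

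| r | Half-width, SD (25 per arm) | Change in width | Power at 0.6 SD (25 per arm) | Chance adjusted interval is narrower (25 per arm) | Power at 0.6 SD (22 per arm) |
|---|---|---|---|---|---|
| unadjusted | 0.569 | – | 54.7% | – | 49.4% |
| 0 | 0.575 | +1.1% | 53.8% | 20% | 48.4% |
| 0.1 | 0.572 | +0.6% | 54.2% | 29% | 48.8% |
| 0.2 | 0.564 | −0.9% | 55.5% | 52% | 50.0% |
| 0.3 | 0.549 | −3.5% | 57.7% | 76% | 52.1% |
| 0.4 | 0.527 | −7.3% | 61.1% | 92% | 55.3% |
| 0.5 | 0.498 | −12.4% | 66.0% | 98% | 60.1% |

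Widths and powers are closed-form. The chance of a narrower interval in a single trial comes from simulation (40,000 trials per scenario).

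**Break-even.** Setting the two widths equal gives r² = 1 − (2.0106/2.0117)²/(1 + 1/46), so r is about 0.15 (0.16 at 22 per arm). Reaching 80% power at 0.6 SD would need r of about 0.68 (0.73 at 22 per arm).

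**Missing PCS.** Suppose 2 of 25 totals per arm are missing at random (an assumption). Simulated power for r = 0/0.1/0.2/0.3/0.4/0.5:

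- no PCS missing: 54.1/54.5/55.9/57.5/61.2/66.4%
- patients without a PCS dropped: 50.2/50.6/52.3/53.9/57.4/62.6%
- overall mean imputed: 54.1/54.4/55.8/57.2/60.6/65.2%

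These compare with each other, and differ from the closed-form column by up to about 0.4 points. Type I error with mean imputation was 5.1%, 5.1% and 5.2% at r = 0, 0.3 and 0.5.

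**The case against.** The strongest reply is that nothing in 10.1.1 is wrong for lack of a covariate, and that the benefit depends on a correlation found nowhere in the documents. The rationale in 6.1 concerns adjustment to pain, not acute pain at 48 hours. For r between 0 and 0.3 the effect is modest, from 1.1% wider to 3.5% narrower, and at r = 0.2 a narrower interval is close to a coin flip. All of this stands. It is why the point is an option and says only that adjustment could help.

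The choice of the PCS is also open to challenge. The LOT-R and the PROMIS anxiety and depression forms are preoperative too, and the protocol plans a combined continuum. Nothing in the documents ranks the PCS first; preferring a simple total to a score derived by scaling is a judgement. Baseline pain may be a better covariate, but its instrument cannot be identified in the text available.

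Finally, the sample size is not consistent across the document: 10.2.2 and 10.2.5 rely on 45 per group. At 45 per arm, unadjusted power at 0.6 SD is 80.4%, adjusted power at r = 0 is 79.9%, and break-even is about 0.11. The cost would then be smaller still, so this does not weaken the suggestion.

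**Conclusion.** The point holds as an optional improvement. The unadjusted test is valid, and the PCS is a true pre-randomisation covariate that the trial already collects. At 25 per arm the downside is about 1 point of power and 1% of width. The gain is nil or slightly negative below |r| of about 0.15, small at 0.2 to 0.3, and useful from about 0.4; the last threshold is a judgement.

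The figures assume a linear relation, a common SD in both arms, 1:1 allocation and an effect of 0.6 SD. They are in SD units and so apply to either definition of the primary endpoint, though r may differ between the two. Adjustment is no remedy for the unsupported 80% power.

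**What to change.** First reconcile the primary endpoint between 5.1.1 and 10.1.1. Then replace the t-test and ANOVA sentences in 10.1.1, before unblinding, with one model:

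> The primary analysis is a linear model of the primary pain outcome on arm and preoperative PCS total (sum of the 13 items, each scored 0–4). The adjusted difference will be reported with its 95% CI and two-sided p-value. A missing PCS total is replaced by the mean of observed totals across both arms, so that no patient in the analysis set is lost for a missing covariate. The unadjusted t-test is a sensitivity analysis.

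The summing rule must be stated because Appendix F, as available, prints a scoring rule for the LOT-R but none for the PCS. Add when a total counts as missing, for example when any item is blank. A preoperative pain score could be a second covariate if its instrument is confirmed, but that too must be fixed before unblinding; the figures above are for one covariate.

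The cost is one paragraph and no new data collection. This wording does not settle who is analysed: the exclusion in 6.1 for an intraoperative decision on axillary dissection can fall after randomisation and must be addressed separately.

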5.2.2 Morphine equivalents used within the first month postoperatively

THE USE OF LIPOSOMAL BUPIVACAINE FOR PAIN CONTROL FOLLOWING MASTECTOMY AND IMMEDIATE IMPLANT BASED BREAST RECONSTRUCTION

Wake Forest Baptist Comprehensive Cancer Center
CCCWU # 99517

- 5.2.2.1 The number of doses of oral narcotics (hydrocodone-acetaminophen 1 tablet) for patients with immediate tissue expander reconstruction without other measure of pain control has been 4.2 at 24 hours and 4.0 at 48 hours¹⁷. This is approximately 3.3 morphine equivalents
- 5.2.2.2 We would expect the patients treated with liposomal bupivacaine to use an average of 2.5 intravenous morphine equivalents at the 48-hour point and decreased morphine equivalents in the liposomal bupivacaine over the first postoperative month.
- 5.2.3 Length of stay for hospitalization after mastectomy and breast reconstruction
 - 5.2.3.1 Length of stay for patients undergoing mastectomy and immediate reconstruction has been shown to be 41-47 hours on average²¹
 - 5.2.3.2 We believe liposomal bupivacaine will shorten this time to 36 hours±12 in the liposomal bupivacaine group, but not in the bupivacaine groups.
- 5.2.4 Readmission rates to the hospital within 2 months after mastectomy and breast reconstruction
 - 5.2.4.1 Patients who underwent tissue expander breast reconstruction have a readmission rate of approximately 4.34%²². We anticipate a readmission rate of approximately 2% Patients will be informed that if they are expected to undergo an axillary lymph node dissection at the time of surgery then they will be excluded from the study. Patients who are undergoing sentinel lymph node biopsies will be included in the study, but if their nodes are positive and there is an intraoperative decision to pursue axillary lymph node dissection they will subsequently be excluded from the study.
- 5.2.5 Frequency of postoperative opioid related adverse effects within the first week of surgery. This includes nausea, vomiting, pruritus, allergy, respiratory depression.
 - 5.2.5.1 After immediate breast reconstruction with implants, patients receiving bupivacaine had a 40% incidence of nausea and vomiting. Those not receiving a local anesthetic had a 75% incidence of nausea and vomiting¹⁷
 - 5.2.5.2 We predict a 30% incidence of opioid related adverse events in our liposomal bupivacaine group
- 5.2.6 Trajectory of postoperative recovery from pain within the first 2 months

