The study will be double blinded to both patients and providers including plastic and general surgeons involved in their operative care. We will enroll our patients in pharmacy randomization program, in which the pharmacy will deliver the appropriate medication per assigned group.

To monitor our primary outcomes, patients will be asked to rate their pain level on a visual analog scale (Table 2, Appendix Z) with activity every 12-hours after surgery during their post-procedure stay. The activity for which they will rate their pain will be the arm movements associated with eating. In the hospital, their visual analog scores will be provided to each patient in person by their nurse every 12 hours. Subject's pain scores will continue to be recorded every 12 hours via a phone call from a study team member for the first 48 hours after discharge. Additionally, while in the hospital, the amount of narcotics used will be recorded and converted into morphine equivalents.

Upon discharge, patients will be given a sheet to record their pain level and the amount of narcotics & benzodiazepines used (Appendix K). Both the amount of narcotics & benzodiazepines and the pain level are to be reported at the time of taking any narcotics & benzodiazepines. Patients will follow up with our clinic at 1 week, 3 weeks, and 5 weeks postoperatively. At week 1 patients will bring in their medication and pain diary, and fill out a pain assessment (Appendix G) in addition to a questionnaire assessing breast cancer surgery

THE USE OF LIPOSOMAL BUPIVACAINE FOR PAIN CONTROL FOLLOWING MASTECTOMY AND IMMEDIATE IMPLANT BASED BREAST RECONSTRUCTION

Wake Forest Baptist Comprehensive Cancer Center
CCCWU # 99517

disability (Appendix H)²³. During subsequent appointments made at 3 and 5 weeks postoperatively, they will be assessed and receive the pain assessment and breast cancer surgery disability assessments as well. When tissue expansion is initiated will be determined by the primary surgeon, but we will track the dates of the initiation of expansion as this will impact pain scores within the electronic medical record.

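### The primary t-test drops any patient without a 48-hour score although earlier scores are scheduled; this costs a little precision and can bias the comparison if loss relates to pain differently by arm

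*Combined protocol and SAP*

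**What the plan says.** Section 10.1.1 names the single score observed at 48 hours as the primary outcome and states "To test for differences in these scores between the 2 arms, an independent t-test will be used". The same paragraph says "The study will allow for an attrition rate of 10" per cent. It then mentions a two-sided ANOVA without giving its factors or endpoint.

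Sections 2.1.1 and 5.1.1 define the outcome differently, as mean pain over the first 48 hours. On the schedule, 5.1.1 says "This will be measured every 12 hours for the first 48 hours", which gives scores at 12, 24, 36 and 48 hours. Section 6.1 has nurses collect them in hospital; after discharge, "pain scores will continue to be recorded every 12 hours via a phone call". On length of stay, 5.2.3.1 cites 41–47 hours, and 5.2.3.2 says "We believe liposomal bupivacaine will shorten this time to 36 hours" (±12), a change not expected with bupivacaine.

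No section gives an analysis population, a rule for missing scores or a sensitivity analysis.

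**The concern.** With no other rule stated, an independent t-test on the 48-hour score is a complete-case analysis. It ignores whatever earlier scores a lost patient has, and in general it is valid only if a missing 48-hour score is unrelated to pain within each arm. A likelihood-based repeated-measures analysis needs less: loss must be explained by arm and the recorded scores.

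The 48-hour score also falls near the change from bedside to telephone collection, and the plan expects discharge times to differ by arm. At stake are a small part of the precision of a 25-per-arm trial, a possible bias of unknown size, and an exclusion rule that nobody has written down before the data are seen.

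**Working it through.** **The plan's own figures.** Section 10.1.1 works "with a 2-sided alpha of 0.05 and power of 80" per cent, and gives a detectable effect "of 0.6 between the 2 groups with 25 subjects per arm"; without attrition, "the study would have the ability to detect an effect size of 0.57". These do not reproduce. For a two-sample t-test, 0.6 SD needs 45 per arm and 0.57 SD needs 50 (45/0.9 = 50). With 25 per arm the detectable effect is 0.81 SD, and power at 0.6 SD is 54.7%. With 10% loss, 25 × 0.9 = 22.5 per arm, the detectable effect is 0.85 SD and power at 0.6 SD is 50.3%. That discrepancy is a separate and larger matter; the figures serve here as the baseline.

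**Precision.** The documents give no within-patient correlation, so I take ρ = 0.5 to 0.7. The share R² of the 48-hour variance explained by the three earlier scores is:
- equal correlations, R² = 3ρ²/(1 + 2ρ): 0.75/2 = 0.375 and 1.47/2.4 = 0.61;
- first-order autoregressive, R² = ρ²: 0.25 and 0.49.

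If the lost patients have all three earlier scores, effective n ≈ 22.5 + 2.5 × R²:
- lowest: 22.5 + 2.5 × 0.25 = 23.1;
- highest: 22.5 + 2.5 × 0.61 = 24.0.

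The standard error falls by 1 − √(22.5/23.1) = 1.3% to 1 − √(22.5/24.0) = 3.2%. Power at 0.6 SD rises from 50.3% to 51.3% at the low end and about 53% at the high end.

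**Where the 48-hour score is collected.** Assume normal stays with SD 12 hours, given only for the liposomal arm and borrowed for the control arm.
- Home by 48 hours: liposomal Φ((48 − 36)/12) = 84%; control Φ((48 − 41)/12) = 72% to Φ((48 − 47)/12) = 53%.
- Home by 36 hours: half of the liposomal arm, Φ(0) = 50%.

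The mode of collection may therefore differ by arm. The schedule in Section 6.0 also labels the 12-hourly scores by time since discharge. If calls are timed that way, a patient discharged at 41–47 hours is first called at 53–59 hours and may have no score at 48 hours.

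**Bias.** I simulated four correlated scores with the correlations above, large samples, SD 2 and 11% of 48-hour scores missing. Loss followed a logistic rule on the recorded 36-hour score, with log odds of 1 per SD. All of these are assumptions.

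| Loss pattern | Complete-case bias (points on 0–10) | Likelihood estimate |
|---|---|---|
| Same mechanism and rate in both arms | about 0 | about 0 |
| Related to pain in one arm only | about 0.10–0.14 | about 0 |
| Opposite directions in the two arms | about 0.2–0.3 | about 0 |

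Bias scales with the SD. The one-arm case is 0.05–0.07 SD, so SDs of 1.5 to 2.5 give 0.05 × 1.5 = 0.08 to 0.07 × 2.5 = 0.18 points. With a stronger rule (log odds 2) and 10% loss, the one-arm case is about 0.07–0.10 SD, or 0.14–0.20 points at SD 2.

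A shared mechanism can still give unequal rates when there is a true effect. With a true effect of 0.6 SD and 10% overall loss, rates of about 12–14% against 6–8% gave a bias of about 0.02–0.07 SD, or 0.04–0.14 points at SD 2.

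The likelihood estimate is unbiased here because loss was generated from recorded scores. When loss depended on the unseen 48-hour score, up to about 0.11 SD of bias remained under the model, against about 0.15 SD for complete cases.

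**If the 48-hour mean is kept.** The plan states no rule for an incomplete set. If all four scores were required and misses were independent (assumed), 5% missing per score would leave 25 × 0.95⁴ = 20.4 per arm, and 10% would leave 25 × 0.90⁴ = 16.4.

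**The case against.** The case on the other side is substantial.

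- **The 10% is an allowance.** A reader might infer that the trial plans to lose 10% of its 48-hour scores. Section 10.1.1 only makes room for attrition in the sample size. This stands.
- **Earlier scores are scheduled, not assured.** A reader might assume that every lost patient has three earlier scores. Patients excluded in surgery after a decision for axillary dissection (Section 6.1) may have no postoperative score, and no model recovers them. This stands.
- **The 48-hour score need not be the weak one.** Calls continue for 48 hours after discharge, so for the expected stays 48 hours lies within active follow-up. About half of the liposomal arm would already be home by 36 hours. This stands: a gap at 48 hours is plausible, not shown.
- **The larger biases need an unlikely mechanism.** The trial is double-blind with one collection procedure. Earlier discharge could change the amount of loss by arm, but nothing suggests that it reverses the direction. The opposite-direction result is a stress case only.
- **The precision gain is small** beside the sample-size discrepancy in the same paragraph. This stands.
- **The endpoint conflict comes first.** It does, but either endpoint needs a rule for missing scores, and one model serves both. The secondary area under the curve and growth curve use repeated scores without changing the primary test, and the unspecified ANOVA does not fill the gap.

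**Conclusion.** The point holds in a limited form. Under 10.1.1 a patient without a 48-hour score drops out of the primary test, and any earlier scores go unused there. On assumed correlations of 0.5–0.7 and 10% loss, the cost is about 0.6 to 1.5 patients' worth of information per arm (23.1 − 22.5 to 24.0 − 22.5).

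A reader might go further and conclude that pain-related loss does bias the comparison. The documents do not support that: they give no pattern of loss, no SD for the pain score and no within-patient correlation. The bias ranges from nothing to a few tenths of a point on the 0–10 scale, depending on assumptions that only the data could inform. The main gain from the change is a rule fixed in advance that protects against loss explained by recorded pain. It does not protect against loss that depends on pain nobody recorded.

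**What to change.** 1. Reconcile the primary endpoint between Sections 2.1.1 and 5.1.1 (48-hour mean) and 10.1.1 (single 48-hour score).
2. In 10.1.1, replace the t-test with a mixed model for repeated measures on the 12-, 24-, 36- and 48-hour scores, with arm, time and arm-by-time, an unstructured covariance and Kenward-Roger degrees of freedom. Include all randomised patients with at least one postoperative score. Take the average-over-time contrast or the 48-hour contrast to match the endpoint kept.
3. Keep the t-test as a supportive analysis.
4. Add a sensitivity analysis for loss that depends on unseen pain, for example delta-adjusted imputation.
5. Report by arm the patients with no postoperative score, since the model cannot recover them.

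The cost is plan wording and some programming, with no new data. The downside is a slightly more complex model that assumes data are missing at random. With complete data its estimate is essentially that of the t-test. The change should be made before unblinding.
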